 - a. Travel across time zone in 2 weeks prior to enrollment or planned during study
 - b. Greater than 6 cups of coffee per day
 - c. Greater than 15 cigarettes per day
 - d. Unwilling to limit alcohol, nicotine, and caffeine consumption during study
5. Adherence factors:
 - a. Ability to adhere to study procedures completed between screening and randomization visits

Off-Study Criteria:

Subjects will be dropped from the study if any of the following:

1. Meeting criteria for a current episode of major depression on the Patient Health Questionnaire 9 (PHQ-9) or depressive symptoms that are deemed by the psychiatrist investigator to be too severe to continue with study procedures
2. Emergence of suicidal ideation; homicidal ideation, or psychotic symptoms
3. Initiation of stimulants, medications for sleep, hormonal medications, or other contraindicated medications
4. Evidence of abuse or misuse of study medications
5. Development of any significant medical problem
6. Pregnancy
7. Enrollment in another clinical trial involving study procedures or medications that might put subject at risk for drug interactions or interfere with study procedures.
8. Significant deviation from study protocol or protocol violation
9. Serious side effect from study medication
10. Inability to tolerate a minimum dose of 10-mg/day of suvorexant

Participants who are dropped from the study will be asked to complete final questionnaires remotely. In this case, vitals will not be collected, and adverse event monitoring will be completed over the phone.

Source of Subjects & Recruitment Methods

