answer questions will be thanked for their time and the phone call will end. Women may ask to stop the screening phone call at any time. The pre-screen questionnaires will be administered to assess insomnia status. The full written ISI will be administered at Visit 3 and Visit 4. The ISI may be administered again over the phone before Visit 1 or Visit 2, if one of these visits has been delayed, and insomnia status must be reassessed. Preliminary screening determination will include questions modified from the Berlin Questionnaire to exclude women at high risk for obstructive sleep apnea. We will also ask some questions drawn from the PHQ-9 which will be completed at the first visit. The PHQ-2 asks specifically about frequency of anhedonia and depression in the past two weeks. We will exclude participants who do not qualify initially on the phone screen. Anyone identified as being at risk for depression will be instructed to assess their symptoms with their physician and be offered resources for where they can seek additional help. The full PHQ-9 will be administered at Visit 1, Visit 3, and Visit 4.

Following the screening phone call, women who are interested and preliminarily eligible to complete the screening process will be mailed or emailed the pre-screening materials, a copy of the informed consent and a cover letter describing the pre-screening procedures. The pre-screening materials include hot flash and sleep diaries to be completed at home for 1 week. BWH study staff will call potential participants to determine whether they received these materials and review how to complete them. Women who are currently taking medications to help them sleep will be asked if they are willing to refrain from taking sleep medications for the duration of the study (approx. 6 weeks) beginning with the tracking period. Women who agree to complete the pre-screening diaries will be contacted by phone after ample time has elapsed. During this call, the BWH study staff member will review the diary entries to determine eligibility for the screening visit. The pre-screening diaries are used to reduce subject burden by only scheduling subjects eligible for the screening visit.

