Treatment period: At the Randomization Visit, eligible women will be randomized to 4 weeks of suvorexant or placebo. Pre-treatment symptom measures will be assessed at the Randomization Visit and interim and final on-treatment symptom measures will be assessed at the Interim Treatment Visit and Final Treatment Visit, respectively. The primary endpoint measures will be obtained at the Final Treatment Visit, conducted after 4 weeks on treatment. Participants will complete sleep and hot flash diaries for the 4 weeks they are on treatment and will be sent an Actiwatch and Biolog monitor to wear for one week (Actiwatch) and for one 24-hr period (Biolog) before returning them at the Final Treatment Visit. Participants will also be asked to provide saliva samples for two consecutive days in between Visits 1 and 2 and Visits 3 and 4. These samples will be used to measure cortisol. We have implemented these procedures in prior clinical trials

with efficiency and high levels of adherence. Adverse events will be assessed at each study visit using spontaneous-reporting adverse event procedures employed in our other clinical trials.

Intervention design: Suvorexant and identical placebo will be obtained from Merck and stored in the Brigham and Women’s Hospital Research Pharmacy. The Research Pharmacist will generate a confidential randomization schema using a block size of 4 to balance the one-to-one treatment assignment between the two study arms. Study participants and all study personnel, including those entering data, will be blinded to the assignment. Only the Research Pharmacist will be unblinded to treatment assignment.

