At the Randomization Visit, a one-week supply of suvorexant 10-mg pills or identical placebo will be given to each participant. Participants will be instructed to start taking 10-mg nightly for the first 7 days. At the Interim Treatment Visit conducted after one-week on treatment, participants who do not have treatment-limiting side effects will be instructed to increase the dose to 20-mg nightly. After the Interim Treatment Visit, women unable to tolerate a 20-mg dose will be given the option to reduce to a 10-mg dose. Consistent with FDA-approved directions, suvorexant will be started at 10-mg to first establish tolerability and then expected treatment efficacy will be optimized by increasing to the target 20-mg dose 7 days later. Any unused medication will be returned at the Final Treatment Visit, and unused pills will be counted as an indicator of adherence. If participants are unable to attend the Final Treatment Visit in person, subjects will complete remaining study procedures remotely, and will mail back any unused medication for a measure of adherence. Participants will also return the Actiwatch, Biolog monitor, and saliva samples by mail if a remote Final Treatment Visit is performed. In addition to answering questionnaires remotely, a study clinician will call the participant for safety monitoring. Study staff will review responses to the PHQ9 before ending study visits, and a study clinician will query participants directly about suicidal ideation and other adverse events at study visits while participants are on medication. Participants will not be informed of their treatment assignment at the Final Treatment Visit to maintain the blinding for study personnel.

Protocol Schema

[figure not shown]

Table of Procedures

		Screening		Intervention		
		Pre-V1	V1	V2 Random-ization	V3	V4
Study Week		-1	0	1	2	5
Weeks on Medication				0	1	4
Visit Location		Phone + Mail	Office	Office	Office	Office
General/ Screening Assessment	Screening Consent	X				
	Written Informed Consent		X			
	Health and Personal History Questionnaire		X			
	Insomnia Diagnostic Assessment		X			
	Medical History		X			
	Concomitant Medications	X	X	X	X	X
	Screening Assays (hepatic, renal, HCG, tox)		X			
	Hormone Assays (FSH, estradiol, progesterone)		X			
	Berlin Questionnaire	X				
Neck circumference		X				
PHQ-2	X					
Vitals	Height/Weight/Heart rate/Blood Pressure		X	X	X	X
	Waist to Hip Ratio		X			
Medication Dispensing & Instructions				X	X	
AE Reporting			X	X	X	X

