 6. Pre-Sleep Arousal Scale (PSAS), a 16-item self-rated scale that generally assesses physiological and cognitive arousal prior to sleep.²⁸
 7. Dysfunctional Beliefs and Attitudes about Sleep (DBAS), a 30-item self-rated scale about cognitions related to sleep (e.g., expectations, consequences).²⁹
 8. Sleep Locus of Control Scale, an 8-item self-rated scale that measures perception of control of sleep as being internal or by chance.³⁰
 9. Hyperarousal Scale, a 26-item self-rated scale of alertness during wake that is widely used to measure trait arousal.³¹
2. Sleep apnea will be screened out using a combination of self-reported prior diagnosis and the following study procedure to exclude women likely to have apnea:
 1. The Berlin Questionnaire, a validated 10-item questionnaire to assess risk of obstructive sleep apnea.^{32,33}
3. Mood, anxiety, and quality of life symptoms will be measured using the:
 1. Patient Health Questionnaire 9-item (PHQ-9), an 9-item self rated measure of depression based on DSM criteria that assesses the core psychological and neuro-vegetative symptoms of depression occurring over the past 2 weeks.³⁴
 2. Center for Epidemiological Studies Depression Scale (CES-D), a 20-item self-rated scale (range 0–60) that measures the severity of predominantly psychological symptoms of depression experienced over the past week.³⁵
 3. Anxiety Sensitivity Index (ASI-3), an 18-item self report questionnaire (range 0–72) assessing sensitivity to the experience of anxiety as an indicator of anxiety and psychological hyperarousal.³⁶
 4. Generalized Anxiety Disorder Questionnaire (GAD-7): The GAD-7 is a 7-item self-report measure frequently used in clinical and research settings to identify four of the most common anxiety disorders in primary care: generalized anxiety, panic, social anxiety, and posttraumatic stress disorder.³⁷
 5. Menopause-Specific Quality-of-Life Questionnaire (MENQOL), a widely used 33-item self-rated questionnaire about quality-of-life specifically in menopausal women.³⁸
 6. The Clinical Global Impression (CGI) and Patient Global Impression (PGI), which are widely used 2-item clinician-rated and patient-rated measures, respectively, which are used to assess global severity of illness and change in a patient over time. They are widely used in clinical trials for depression, fatigue, and other neuropsychological endpoints.

4. Hot flashes will be measured using:

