 1. Hot flash diaries will be completed twice daily (morning and night) to capture the number of hot flashes, their severity, and how bothersome they are.³⁹
 2. The Biolog skin conductance hot flash monitor (UFI, Morro Bay, CA) is a widely used and validated ambulatory monitor that will be worn to quantify the number of objectively measured hot flash events by detecting changes in skin conductance on the sternum. This approach measures physiologic hot flashes independent of recall for the events, thereby eliminating potential recall bias for nighttime events.
 3. The Hot Flash Related Daily Interference Scale (HFRDIS) is a 10-item self-rated scale (range 0–100) that measures the degree to which hot flashes interfere with daily activities and quality-of-life during the prior week.⁴⁰

Drugs to be used

This study will compare the effect of suvorexant 10–20 mg to placebo on insomnia symptoms in peri- and postmenopausal women who have an insomnia syndrome related to nighttime hot flashes. Up to seventy-two women will be randomized in a 1-to-1 ratio to suvorexant 10–20 mg or equivalent placebo (see Schema) in order to have 60 women (30 per arm) complete the trial, after allowing for post-randomization drop-outs.

Eligible women will be randomized to 4 weeks of suvorexant or placebo after a 1-week screening period and a one-week screening run-in period. Participants will complete 4 in-person study visits (consent / screening visit, randomization visit, one-week on-treatment visit, and a final week-4 on-treatment visit) and one telephone-based initial screening assessment. Suvorexant will be started at 10-mg nightly for the first 7 days. After one-week of treatment, the dose will be increased to 20-mg nightly unless there are dose-limiting side effects. Women unable to tolerate a 20-mg dose will be given the option to reduce to a 10-mg dose.

Known toxicities of suvorexant include daytime somnolence, nighttime “sleep driving”, worsening of depression or suicidal thinking, compromised respiratory function, sleep paralysis, hypnagogic/hypnopompic hallucinations, and cataplexy-like symptoms.

Devices to be used

Actiwatch actigraphic Watch: This is an actigraphic watch (Philips Respironics, Murrysville, Pennsylvania) that will be worn on the non-dominant wrist to quantify sleep patterns based on acceleration and movement data. The data output will be analyzed using standard actigraphic analysis algorithms.

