A Medical Monitoring Checklist has been developed to be included with each participant's binder, which triggers the Medical Monitor to double-check lab results, vital signs, concomitant medications, adverse events, and the scores on the Patient Health Questionnaire-9 (PHQ-9) at all visits.

Additional measures for assessing suicidal ideation

Several measures are in place to assess for suicidal ideation in participants throughout the study.

1. The Informed Consent form includes a statement informing participants to let study staff know if at any time they experience thoughts of self-harm or suicidal ideation during the study. The consenting clinician verbally confirms this statement prior to the participant signing the form.
2. Participants are screened by a study clinician for current Major Depressive Disorder and/or suicidal ideation at the Screening Visit after consent. Both are exclusion criteria for continued participation in the study. If excluded for depression or suicidal ideation, participants would be assessed by a study clinician for need for urgent care and referred to mental health services for treatment.
3. Participants complete the PHQ-9 at study visits while on medication. The PHQ-9 is completed on an iPad during the study visit. If a participant indicates thoughts of self-harm or suicidal ideation on the PHQ9, an alert is set to immediately send an email to the Principal Investigator, the Medical Monitor, the Sr. Project Manager, and the Research Coordinator.

4. Study staff review the responses to the PHQ9 before ending the study visit.
5. A study clinician will query participants directly about suicidal ideation and will inquire about adverse events at study visits while participants is on medication.
6. Any participant indicating emergence of suicidal ideation as determined by a study clinician will be taken off-study and referred to mental health services for further treatment.

Independent Safety Monitor

[REDACTED], will serve as the Independent Safety Monitor (ISM) for the remainder of this trial. The plan for Independent Safety Monitoring is as follows:

- In the case of a Serious Adverse Event (SAE), the study team will notify the ISM within 24 hours of becoming aware of the SAE. The ISM will review the case and, if appropriate, will examine the participant. The ISM will produce a short report on the SAE.

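### The PHQ-9 is to be checked at all visits but is not scheduled at the Randomization Visit, so the last scheduled PHQ-9 or suicidal-ideation check before the first dose is at screening, nominally one week earlier.

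*Combined protocol and SAP*

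**What the plan says.** Section IX, Medical Monitoring Plan, describes a checklist that prompts the Medical Monitor to double-check laboratory results, vital signs, concomitant medications, adverse events and "the scores on the Patient Health Questionnaire-9 (PHQ-9) at all visits".

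Section IV, Pre-Screening, sets the schedule: "The full PHQ-9 will be administered at Visit 1, Visit 3, and Visit 4". The PHQ-9 row of the Table of Procedures agrees, with marks at V1, V3 and V4 and a blank at V2. Section IX, on suicidal ideation, adds: "Participants complete the PHQ-9 at study visits while on medication".

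Section V, Treatment period, says: "Pre-treatment symptom measures will be assessed at the Randomization Visit". The table marks the CES-D, ASI-3 and GAD-7 at that visit, but not the PHQ-9.

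Section III makes a current major depressive episode (with the PHQ-9 as an indicator) and current suicidal ideation exclusions. Its Off-Study Criteria use the PHQ-9 again. Section V, Drugs to be used, lists "worsening of depression or suicidal thinking" among the known toxicities.

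The instrument description in Section V says that the PHQ-9 covers "symptoms of depression occurring over the past 2 weeks". V3 is timed as follows: "At the Interim Treatment Visit conducted after one-week on treatment".

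**The concern.** The PHQ-9 serves as an eligibility indicator, an off-study trigger and the carrier of the self-harm alert. The plan asks for it to be checked at every visit, yet does not collect it at the visit where the decision to randomise is made. Nothing else scheduled at V2 fills that role. The definitive eligibility review (Sections IV and V) names only the sleep diary and laboratory results, and the clinician's direct question about suicidal ideation starts once a woman is on medication.

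Two things are at stake. First, a woman whose mood worsened or who developed suicidal ideation during the run-in week could be randomised without a scheduled check that would show it. Second, if the V3 PHQ-9 is raised, there is no PHQ-9 score from just before dosing to help separate run-in deterioration from on-drug deterioration, and such worsening is a listed toxicity.

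**Working it through.** The plan states no figure on this point, so the check is a comparison of sections plus calendar arithmetic.

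**1. Does the checklist have something to check at V2?**

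| Checklist item | Available at V2? | Source |
|---|---|---|
| Laboratory results | Yes: drawn at V1, reviewed at V2 before randomisation | Sections IV and V |
| Vital signs | Yes | Table of Procedures |
| Concomitant medications | Yes | Table of Procedures |
| Adverse events | Yes | Table of Procedures |
| PHQ-9 | No | Section IV; Table of Procedures |

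Four of the five items have content at V2. Only the PHQ-9 has none.

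**2. When is depression or suicidal ideation checked?**

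| Check | V1 | V2 | V3 | V4 |
|---|---|---|---|---|
| PHQ-9 | X | – | X | X |
| Clinician screen for major depression and suicidal ideation (Section IX) | X | – | – | – |
| Direct clinician question on suicidal ideation (Sections V and IX) | – | – | X | X |
| CES-D | – | X | X | X |

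**3. Calendar.** From the Table of Procedures, V1 = study week 0, V2 = week 1 (0 weeks on drug), V3 = week 2 (1 week on drug) and V4 = week 5 (4 weeks on drug). I assume that dosing starts at V2. PHQ-9 recall is 2 weeks.

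- Gap from last PHQ-9 to first dose: week 1 − week 0 = 1 week = 7 days.
- V3 window: weeks 0 to 2, of which weeks 0 to 1 are pre-dose. Pre-dose share = 7/14 = 50%.
- V4 window: weeks 3 to 5, wholly on treatment.
- If V2 slips by d days and V3 stays one week after dosing, the gap becomes 7 + d days. The V3 window then starts d days after V1, so those d days fall within no PHQ-9 window. Section IV foresees delayed visits and allows the ISI to be repeated before a delayed V2. It states no equivalent for the PHQ-9 or suicidal ideation.

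**4. Effect of adding a V2 score.** Its window would be weeks −1 to 1, wholly pre-dose. The V3 window would still be weeks 0 to 2 and 50% pre-dose. The overlap comes from using a 2-week recall after 1 week on drug, and adding V2 does not change it.

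**The case against.** The strongest reply is that the two places that set the schedule agree exactly, and that the checklist sentence is loose wording for whatever each visit collects. Laboratory tests are in the same sentence and are drawn only at V1. This softens the conflict. It explains V2 less well, because laboratory results are reviewed there and the PHQ-9 is the only item with nothing behind it.

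There are other safeguards. The CES-D at V2 covers the past week, which is nominally the run-in week. Adverse events are recorded at V2. Women are told at consent to report thoughts of self-harm. The Medical Monitor reviews safety data from all visits within 2 business days. These are real, but the CES-D is listed as exploratory with no stated eligibility threshold or alert, and the reporting routes depend on the woman volunteering the information.

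A reader might also infer more than the documents support:

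- *That depression is not reassessed at all before dosing.* The CES-D at V2 contradicts this. What is missing is a PHQ-9 or suicidal-ideation check tied to eligibility.
- *That omitting V2 causes the mixed V3 window.* It does not; the mixing would remain with a V2 score.
- *That women dropped at V3 lose their Week-4 data.* Section III says dropped participants are asked to complete final questionnaires remotely. Some may not, but loss is not automatic.
- *That the PHQ-9 has no baseline, or that an endpoint is compromised.* A pre-dose V1 score exists. The exploratory endpoint is simply depressive symptoms, and no PHQ-9 change analysis is specified.
- *That safety comparisons between arms are biased.* The pre-dose week enters the V3 score in both randomised arms, so no such bias is shown.

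**Conclusion.** The point holds as an internal inconsistency with a modest safety consequence. The checklist and the PHQ-9 schedule do not agree for V2, and no scheduled PHQ-9 or suicidal-ideation check falls between V1 and the first dose. The gap is nominally 7 days and longer if V2 is delayed.

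Up to 72 women would be randomised without a V2 PHQ-9. That figure counts women lacking the form, not women harmed. The documents give no rate at which women would newly meet an exclusion during the run-in, so the number affected cannot be estimated.

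The primary ISI endpoint and the sample-size calculation are not touched. The conclusion assumes that visits follow the Table of Procedures and that no unstated mood or suicidality review takes place at V2.

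**What to change.** Reconcile Section IV (Pre-Screening), Section V (Treatment period), the Table of Procedures and Section IX. There are two ways to do it.

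- **Preferred:** mark the PHQ-9 at V2 in the table and in Section IV, completed and reviewed before randomisation under the plan's existing criteria. Section IX describes the self-harm alert in the item about visits on medication, so it should say that the alert also operates at V2. Name the V2 score as the PHQ-9 baseline.
- **Minimum:** reword the checklist to name the visits at which the PHQ-9 is collected, and state that V1 is its baseline. This removes the contradiction but leaves the pre-dose gap.

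The preferred change costs one nine-item self-report form at a visit already held, plus edits to the text and table. A few women may be found ineligible at V2. What should follow clinically from a V2 score is for the sponsor and the investigator to decide; no new threshold or rule is proposed here.
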